9.7 Validation of Statistical Analyses

Programs will be developed and maintained, and output will be verified in accordance with current risk-based quality control procedures.

Tables, figures, and listings will be produced with validated standard macro programs where standard macros can produce the specified outputs.

The production environment for statistical analyses consists of Amgen-supported versions of statistical analysis software, for example the SAS System.

10. Statistical Methods of Analysis

10.1 General Principles

Descriptive statistics for continuous variables, consists of number of observations, mean, standard error and/or SD, median, 25th percentile (Q1), 75th percentile (Q3), minimum, maximum, and for categorical variables, the number of observations, frequency, and percentage will be presented. Subject disposition, demographics, baseline characteristics, and safety information will be summarized. There will be no adjustment for multiplicity and no imputation techniques for missing values. All analyses will be based on observed data.

10.2 Subject Accountability

A summary of subject disposition with discontinuation reasons, and etanercept completion and discontinuation will be provided. A list of subjects who withdraw early will be provided. It will include the reason and timing of the withdrawal. Similarly, the reason any subject is excluded from an analysis set will also be provided. In addition, significant known protocol deviations will be noted for individual subjects.

10.3 Important Protocol Deviations

Important Protocol Deviations (IPDs) categories are defined by the study team before the first subject's visit and updated during the IPD reviews throughout the study prior to database lock. These definitions of IPD categories, sub-category codes, and descriptions will be used during the course of the study. Eligibility deviations are defined

in the protocol. The final IPD list is used to produce the Summary of IPDs table and the List of Subjects with IPDs.

10.4 Demographic and Baseline Characteristics

Age, race, sex, height, weight, baseline PGA, prior biologic use and indication will be summarized for all the subjects enrolled.

10.5 Primary Analyses

A mixed effects analysis of variance model will be used for the primary endpoint. Treatment, period, sequence and disease indication (RA or PsA) will be evaluated as fixed effects, and subject nested within sequence will be included as a random effect. The modified formulation of etanercept will be used as the test treatment and current formulation of etanercept as the reference treatment.

The null hypothesis that there is no difference of injection site pain between the current and modified formulation will be tested and p-value will be provided. The least square mean of the injection site pain score and the difference between the formulations will be estimated and the corresponding 2-sided 95% CI will be provided..

10.6 Other Analyses

The descriptive statistics will be provided for the injection site pain score for overall and by indication and formulation.

Sensitivity analyses will be performed for the primary endpoint for subjects in the primary analysis set, excluding the subject(s) with injection(s) administrated without warming the investigation product to the required temperature.

Subgroup analyzes will be conducted for the primary endpoint with the subgroups defined in [Section 4.2](#).

10.7 Safety Analyses

10.7.1 Adverse Events and Disease Related Events

The Medical Dictionary for Regulatory Activities (MedDRA) version 19.0 or later will be used to code all events categorized as adverse events (AEs) to a system organ class and a preferred term. The severity of each adverse event will be graded using CTCAE version 4.0 criteria.

The subject incidence of AEs will be summarized for all treatment-emergent AEs, serious AEs, AEs leading to withdrawal of investigational product, fatal AEs.

Subject incidence of all treatment-emergent AEs, serious AEs, AEs leading to withdrawal of investigational product, and fatal AEs will be tabulated by system organ class and preferred term in descending order of frequency.

Summaries of treatment-emergent and serious adverse events will be tabulated by system organ class, preferred term, and grade in descending order of frequency.

Adverse events (such as injection site reactions) occurring during different periods of the treatment may be examined to evaluate the safety and tolerability of a current formulation versus the modified formulation of etanercept.

10.7.2 Laboratory Test Results

Drug-induced liver injury will be assessed by evaluating subjects for Hy's Law in the study period. Hy's law lab value criteria is defined as aspartate amino transferase or alanine amino transferase > 3 times upper limit of normal (ULN), total bilirubin > 2 times ULN, and alkaline phosphatase < 2 times ULN assessed within 7 days. Subjects who meet these criteria on study will be further evaluated to assess whether there exist underlying conditions or concomitant medications which can explain the elevation in laboratory analytes.

Individual chemistry, hematology laboratory data will not be listed unless any safety issue arises.

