- Subjects with a positive PPD test (without a history of Bacillus Calmette-Guérin vaccination) or subjects with a positive or indeterminate Quantiferon test are allowed if they have ALL of the following:
 - no symptoms per tuberculosis worksheet provided by Amgen
 - documented history of a completed course of adequate prophylaxis (completed treatment for latent tuberculosis) per local standard of care before the start of investigational product
 - no known exposure to a case of active tuberculosis after most recent prophylaxis

214 Subject has 1 or more significant concurrent medical conditions per investigator judgment, including the following:

- poorly controlled diabetes
- chronic kidney disease stage IIIb, IV, or V
- symptomatic heart failure (New York Heart Association class II, III, or IV)
- myocardial infarction or unstable angina pectoris within the past 12 months before randomization
- uncontrolled hypertension
- severe chronic pulmonary disease (eg, requiring oxygen therapy)
- multiple sclerosis or any other demyelinating disease
- major chronic inflammatory disease or connective tissue disease other than RA or PsA (eg, fibromyalgia, systemic lupus erythematosus with the exception of secondary Sjögren's syndrome, etc.)

Excluded Medications

215 Subject has used biologic disease modifying agent \leq 3 months before screening

216 If subject is receiving continuous treatment with acetaminophen, non-steroidal anti-inflammatory drug or tramadol, hydrocodone, oxycodone, codeine, and/or propoxyphene and the dose is within 4 hours before study visit and dose is not stable for \geq 2 weeks before first dose of investigational product

217 For subjects not on continuous analgesics, subject has taken the following within 4 hours before screening: acetaminophen, non-steroidal anti-inflammatory drugs, hydrocodone, codeine, tramadol, propoxyphene, and/or oxycodone (unless in the form of OxyContin). For subjects not on continuous analgesics, subject has taken OxyContin within 24 hours before screening.

218 Subject has received live vaccines \leq 4 weeks before first dose of investigational product

Laboratory Abnormalities

219 Subject has laboratory abnormalities during screening, including the following:

- Aspartate aminotransferase (AST) and/or alanine aminotransferase (ALT) $> 1.5 \times$ the upper limit of normal (ULN)
- Platelet count $< 125,000/\text{mm}^3$ (or $125 \times 10^9/\text{L}$)

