7.1 Schedule of Assessments

Table 1. Schedule of Assessments

	Screening	Double-blind Treatment Period		Safety Follow-up/EOS
Days	-14 to -1	1 (\pm 3 days)	8 (\pm 3 days)	38 (\pm 7 days)^a
GENERAL & SAFETY ASSESSMENTS				
Informed consent	X			
Demographic data	X			
Registration via IVR/IWR	X			
Eligibility criteria	X			
Medical history	X			
Medication history	X			
Concomitant medications	X	X	X	
Adverse events ^b	X	X	X	
Serious adverse events ^b	X	X	X	X
Physical examination ^c	X	X	X	
Vital signs	X	X	X	
Weight	X			
Height	X			
Chest x-ray (if needed) ^d	X			
LABORATORY ASSESSMENTS				
Serum pregnancy test ^e	X			
Pregnancy test (urine) ^e		X		
Hematology profile	X			
Chemistry profile	X			
Tuberculosis testing ^f	X			
Hepatitis B and C serologies ^g	X			
DOSING				
Investigational product dispensation (etanercept)		X	X	
DISEASE ASSESSMENTS				
Physician global assessment of disease activity (VAS 0-100)	X	X	X	
SUBJECT ASSESSMENTS (Reported Outcomes)				
Injection site pain (VAS 0-100)		X	X	

Footnotes defined on next page.

EOS = end-of-study, IVR = interactive voice response, IWR = interactive web response, PPD = purified protein derivative, TNF = tumor necrosis factor, VAS = Visual Analog Scale

^a Thirty days (+ 7 days) after their last dose of etanercept, subjects will be contacted by phone by the study staff to follow-up on any continuing serious adverse events and inquire about the emergence of any new serious adverse events.

^b Adverse events and serious adverse events are collected from signing the informed consent form. Adverse device effects are included in the collection of adverse events. Adverse events are collected through the end of treatment period.

^c A full physical examination will be completed at the screening visit. Subsequent physical examinations will be conducted per standard of care to monitor for any changes.

^d Only for subjects with a positive tuberculosis test (ie, positive PPD or positive or indeterminate Quantiferon).

^e For all females, unless at least 2 years postmenopausal or postmenopausal status has been confirmed or history of hysterectomy, bilateral salpingectomy, or bilateral oophorectomy.

^f Subjects will receive either a PPD test or Quantiferon test at screening. National guidelines should be followed for appropriate tuberculosis screening in the setting of anti-TNF therapy.

^g Subjects positive for hepatitis B core antibody may require additional testing for hepatitis B DNA by polymerase chain reaction.

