7.2.3 Treatment Period

Visits will occur per the Schedule of Assessments during the treatment period from screening through week 2. Study visits may be completed within \pm 3 days of the target visit date. Prior to enrollment, subject eligibility must be confirmed with screening procedures. Subjects satisfying eligibility requirements will be enrolled. The date of the first dose of investigational product is defined as day 1. All subsequent doses and study visits will be scheduled based on the day 1 date.

The procedures completed during the 2-week treatment period are those listed in **Table 1**. Etanercept is to be administered after all assessments have been done for all visits with the exception of the VAS subject injection site pain assessment.

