7.2.4 Safety Follow-up/End-of-Study

Thirty days (+ 7 days) after their last dose of etanercept, subjects will be contacted by phone by the study staff to follow-up on any continuing serious adverse events and inquire about the emergence of any new serious adverse events.

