7.3.13 Laboratory Assessments

All laboratory samples will be processed and sent to the central laboratory with the exception of urine pregnancy and PPD, which will be done by the site staff, and Quantiferon, which may be done by central or local laboratory. The central laboratory will be responsible for all screening and on-study serum chemistry, hematology, serum pregnancy, hepatitis C antibody, hepatitis B surface antigen and core antibody, and any other laboratory tests required. The results of this testing will be maintained in the source documents at the site. The central laboratory will provide a study manual that outlines handling, labeling, and shipping procedures for all samples. All blood samples will be obtained by venipuncture before investigational product administration. The date and time of sample collection will be recorded in the source documents at the site. Specific analytes for serum chemistry, hematology, and other testing to be conducted on blood and urine samples are listed below. Although not specifically listed, additional components, abnormal, and/or atypical cells will also be reported if present.

Table 2. Laboratory Analyte Listing

Central Lab Chemistry	Central Lab Hematology	Central Lab Other Labs	Local Lab Other Labs	Local/Central Lab Other Labs
Sodium	RBC	Hepatitis B	Urine	Tuberculosis
Potassium	RBC Morphology	surface antigen	pregnancy	testing ^b
Chloride	Hemoglobin	total		
Bicarbonate	Hematocrit	Hepatitis B core		
Total protein	Platelets	antibody		
Albumin	WBC	Hepatitis B virus		
Calcium	Differential	DNA by		
Adjusted calcium	
• Bands/stabs• Eosinophils• Basophils• Lymphocytes• Monocytes• Neutrophil ANC	polymerase		
Magnesium		chain reaction		
Phosphorus		Hepatitis C		
Glucose		antibody		
BUN or Urea		Serum beta		
Creatinine		hCG ^a		
Uric acid				
Total bilirubin				
Direct bilirubin				
Alkaline phosphatase				
AST (SGOT)				
ALT (SGPT)				

Abbreviations: ALT = alanine aminotransferase, ANC = absolute neutrophil count, AST = aspartate aminotransferase, BUN = blood urea nitrogen, hCG = human chorionic gonadotropin, PPD = purified protein derivative, RBC = red blood cell, SGOT = serum glutamic oxaloacetic transaminase, SGPT = serum glutamic-pyruvic transaminase, WBC = white blood count.

^aAll female subjects except those who are confirmed surgically sterile or at least 2 years postmenopausal or per the definition in [Section 6.8](#).

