14. APPENDICES

Appendix A. Additional Safety Assessment Information

Adverse Event Grading Scale

The Common Toxicity Criteria version 4.0 is available at the following link:

http://ctep.cancer.gov/forms/CTCv20_4-30-992.pdf

Drug-induced Liver Injury Reporting & Additional Assessments

Reporting

To facilitate appropriate monitoring for signals of DILI, cases of concurrent AST or ALT and TBL and/or INR elevation according to the criteria specified in [Section 6.3](#) require the following:

- The event is to be reported to Amgen as a serious adverse event within 24 hours of discovery or notification of the event (ie, before additional etiologic investigations have been concluded)
- The appropriate CRF (eg, Event CRF) that captures information necessary to facilitate the evaluation of treatment-emergent liver abnormalities is to be completed and sent to Amgen.

Other events of hepatotoxicity and potential DILI are to be reported as serious adverse events if they meet the criteria for a serious adverse event defined in [Section 9.2.1.2](#).

Additional Clinical Assessments and Observation

All subjects in whom investigational product(s) or protocol-required therapies is/are withheld (either permanently or conditionally) due to potential DILI as specified in [Section 6.3](#) or who experience AST or ALT elevations $> 3 \times$ ULN or 2-fold increases above baseline values for subjects with elevated values before drug are to undergo a period of “close observation” until abnormalities return to normal or to the subject’s baseline levels.

Assessments that are to be performed during this period include:

- Repeat AST, ALT, ALP, bilirubin (total and direct), and INR within 24 hours
- In cases of TBL $> 2 \times$ ULN or INR > 1.5 , retesting of liver tests, BIL (total and direct), and INR is to be performed every 24 hours until laboratory abnormalities improve

Testing frequency of the above laboratory tests may decrease if the abnormalities stabilize or the investigational product(s) or protocol-required therapies has/have been discontinued AND the subject is asymptomatic.

- Initiate investigation of alternative causes for elevated AST or ALT and/or elevated TBL. The following are to be considered depending on the clinical situation:
 - Complete blood count (CBC) with differential to assess for eosinophilia

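### SAP 10.7.2 plans a Hy's Law assessment over the study period, but the protocol schedules no liver tests after dosing

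*SAP*

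**What the plan says.** SAP Section 10.7.2 commits to a hepatic assessment without qualification: "Drug-induced liver injury will be assessed by evaluating subjects for Hy's Law in the study period". A case requires AST or ALT above 3 × ULN, total bilirubin above 2 × ULN and alkaline phosphatase below 2 × ULN, assessed within 7 days. Subjects who meet the criteria are then examined for other explanations. The same section says that individual chemistry and hematology data will be listed only if a safety issue arises.

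The protocol determines which samples exist:

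- Section 7.1, Table 1: the row "Chemistry profile" has one mark, under Screening (Days -14 to -1). The cells for Day 1, Day 8 and Day 38 are empty.
- Section 7.2.3: "The procedures completed during the 2-week treatment period are those listed in" Table 1.
- Section 7.2.4: after the last dose, "subjects will be contacted by phone by the study staff to follow-up on any continuing serious adverse events" and to ask about new ones. No sample is mentioned.
- Section 7.3.13: "The central laboratory will be responsible for all screening and on-study serum chemistry", with no visit attached to the on-study part.
- Section 4.1.2, criterion 219: "Subject has laboratory abnormalities during screening, including the following", where the list includes AST or ALT above 1.5 × ULN.
- Appendix A: "Repeat AST, ALT, ALP, bilirubin (total and direct), and INR within 24 hours". This applies once product has been withheld for potential liver injury or a transaminase elevation has already been found.

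**The concern.** The SAP announces an assessment for which the visit schedule supplies no data. An analyst who follows it would search the database for qualifying results and, in the absence of unscheduled tests, find none. The natural report is that no subject met Hy's Law, and it would be read as a finding about the safety analysis set. It would look the same whether the true risk was nil or substantial, because no scheduled test could have shown otherwise.

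The reporting rules make this hard to see. No count of subjects with post-dose liver results is planned, and chemistry data are not listed by default. The report would therefore give no sign that testing had not been done.

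**Working it through.** The SAP gives no figure to reproduce. The check is a count from the schedule, a comparison of two thresholds, and an illustration of what zero cases can show.

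**1. Scheduled chemistry per subject (Protocol Table 1)**

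| Time point | Chemistry scheduled |
|---|---|
| Screening, Days -14 to -1 | 1 |
| Day 1 | 0 |
| Day 8 | 0 |
| Day 38 follow-up | 0 |

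The total after the first dose is 0 + 0 = 0 (Day 8 and follow-up). Over 112 planned subjects that is 112 × 0 = 0 scheduled post-dose results. The blank cells do not look like an extraction fault: the urine pregnancy row in the same table falls under Day 1 and dispensation falls under Days 1 and 8, as they should. The synopsis calls the follow-up a visit, but Table 1 marks no chemistry there.

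**2. Can the screening sample identify a case?** It precedes exposure, so it cannot show injury caused by study drug. Even if the study period is read to include screening, criterion 219 limits an eligible subject to AST and ALT of at most 1.5 × ULN. The SAP criterion requires more than 3 × ULN. Since 1.5 < 3, no eligible screening value qualifies.

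**3. Other routes to a post-dose result**

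- Section 7.3.13 assigns responsibility to a laboratory. It sets no time point.
- Section 6.3 acts on abnormal hepatic values or on signs and symptoms of hepatitis. It says what to do with a result or a symptom, but schedules no sample.
- Appendix A orders repeat tests after an elevation or a withholding. No scheduled post-dose test would detect the first elevation.

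So scheduled tests can identify 0 cases by design. Any case must come from unscheduled or for-cause testing.

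**4. What zero cases would mean.** If n subjects are tested and none is a case, the exact one-sided 95% upper bound on the risk is 1 − 0.05^(1/n). The documents do not say how many subjects would be tested, so the values of n are assumed:

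| Subjects tested (assumed) | Upper bound |
|---|---|
| 112 | 1 − 0.05^(1/112) = 2.6% |
| 10 | 1 − 0.05^(1/10) = 25.9% |
| 5 | 1 − 0.05^(1/5) = 45.1% |
| 0 | no bound |

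Subjects tested for cause are selected, so even these bounds would not carry over to the whole safety analysis set.

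**The case against.** The strongest reply is that SAP 10.7.2 describes a case review and no more. It plans no rate, interval, comparison of formulations or conclusion on hepatic safety, and the only safety endpoint is adverse events. Listing laboratory data only if an issue arises fits handling by exception. Section 6.3 lets symptoms and investigator judgment lead to withholding, which triggers Appendix A, so for-cause results could exist and the SAP criteria would then apply to them. The words on on-study chemistry in Section 7.3.13 can be read as covering unscheduled samples only. The upper bounds rest on assumed numbers and concern a rate that the SAP never estimates.

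Much of this stands. The sentence is workable as a rule for results that happen to arise, the conflict with Section 7.3.13 depends on how that text is read, and the bounds are illustrations only. None of it creates a scheduled post-dose test. The SAP does not present the evaluation as a for-cause rule: it says that liver injury will be assessed across the study period. Although no rate is planned, following the text would still produce a statement of no cases without the number tested. A reader with both documents open could work out the limit, but the safety output itself would not show it.

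**Conclusion.** The concern holds. Under Table 1 as written, scheduled testing supplies no post-dose liver result for any of the 112 planned subjects and can identify no Hy's Law case whatever the true risk. SAP 10.7.2 claims an assessment that the design does not deliver. This is an error in what the SAP states and goes beyond missing detail.

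The consequence is confined to one safety statement. The primary pain comparison and the adverse event endpoint do not depend on it. The conclusion assumes that Table 1 is the operative schedule, as Section 7.2.3 indicates. If the wording in Section 7.3.13 reflects post-dose chemistry that was intended but left out of the table, the two protocol sections disagree and the conclusion would change with the schedule. How many subjects would have for-cause tests cannot be known from the documents.

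**What to change.** 1. Reconcile first. The sponsor should settle what Table 1, Protocol Section 7.3.13 and SAP 10.7.2 jointly mean for post-dose chemistry. Whether such tests should be scheduled is a clinical decision for the sponsor, and this review takes no position on it.
2. If Table 1 stands, restate SAP 10.7.2 to say that no post-dose liver tests are scheduled, that hepatic safety is not systematically assessed, and that Hy's Law is evaluated only in subjects with post-dose AST or ALT, total bilirubin and alkaline phosphatase results within the 7-day window, whether unscheduled or obtained under Appendix A.
3. Report the number of such subjects as the denominator, and state that zero cases among them is not evidence for the whole safety analysis set.
4. If the reconciled schedule does include post-dose chemistry, revise the limiting statement to match.

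The cost is the sponsor's decision, a few sentences in the SAP and one added count in the safety output. The drawback is a narrower and less favorable hepatic safety statement.

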10.7.3 Physical Examination

The physical examination results will not be listed unless any safety issue arises.

